Appendix C: Medicare National Coverage Decision for Clinical Trials

This national coverage policy is based upon the authority found in §1862(a)(1)(E) of the Social Security Act (Act). It is binding on all Medicare carriers, fiscal intermediaries, Peer Review Organizations, Health Maintenance Organizations, Competitive Medical Plans, Health Care Prepayment Plans, and Medicare+Choice organizations (§1852(a)(1)(A) of the Act). In addition, an administrative law judge may not disregard, set aside, or otherwise review a national coverage decision issued under §1862(a)(1) of the Act. 42 C.F.R. §405.860.

Clinical Trials

Effective for items and services furnished on or after September 19, 2000, Medicare covers the routine costs of qualifying clinical trials, as such costs are defined below, as well as reasonable and necessary items and services used to diagnose and treat complications arising from participation in all clinical trials. All other Medicare rules apply.

Routine costs of a clinical trial include all items and services that are otherwise generally available to Medicare beneficiaries (i.e., there exists a benefit category, it is not statutorily excluded, and there is not a national noncoverage decision) that are provided in either the experimental or the control arms of a clinical trial except:

- the investigational item or service, itself,
- items and services provided solely to satisfy data collection and analysis needs and that are not used in the direct clinical management of the patient (e.g., monthly CT scans for a condition usually requiring only a single scan); and
- items and services customarily provided by the research sponsors free of charge for any enrollee in the trial.

Routine costs in clinical trials include:

- Items or services that are typically provided absent a clinical trial (e.g., conventional care);

- Items or services required solely for the provision of the investigational item or service (e.g., administration of a noncovered chemotherapeutic agent), the clinically appropriate monitoring of the effects of the item or service, or the prevention of complications; and
- Items or services needed for reasonable and necessary care arising from the provision of an investigational item or service--in particular, for the diagnosis or treatment of complications.

This policy does not withdraw Medicare coverage for items and services that may be covered according to local medical review policies or the regulations on category B investigational device exemptions (IDE) found in 42 C.F.R. §405.201-405.215 and §411.15 and §411.406. For information about LMRPs, refer to www.lmrp.net, a searchable database of Medicare contractors' local policies.

For noncovered items and services, including items and services for which Medicare payment is statutorily prohibited, Medicare only covers the treatment of complications arising from the delivery of the noncovered item or service and unrelated reasonable and necessary care. (Refer to MCM 2300.1 and MIM 3101.) However, if the item or service is not covered by virtue of a national noncoverage policy in the Coverage Issues Manual and is the focus of a qualifying clinical trial, the routine costs of the clinical trial (as defined above) will be covered by Medicare but the noncovered item or service, itself, will not.

Requirements for Medicare Coverage of Routine Costs

Any clinical trial receiving Medicare coverage of routine costs must meet the following three requirements:

1. The subject or purpose of the trial must be the evaluation of an item or service that falls within a Medicare benefit category (e.g., physicians' service, durable medical equipment, diagnostic test) and is not statutorily excluded from coverage (e.g., cosmetic surgery, hearing aids).

2. The trial must not be designed exclusively to test toxicity or disease pathophysiology. It must have therapeutic intent.
3. Trials of therapeutic interventions must enroll patients with diagnosed disease rather than healthy volunteers. Trials of diagnostic interventions may enroll healthy patients in order to have a proper control group.

The three requirements above are insufficient by themselves to qualify a clinical trial for Medicare coverage of routine costs. Clinical trials also should have the following desirable characteristics; however, some trials, as described below, are presumed to meet these characteristics and are automatically qualified to receive Medicare coverage:

1. The principal purpose of the trial is to test whether the intervention potentially improves the participants' health outcomes;
2. The trial is well-supported by available scientific and medical information or it is intended to clarify or establish the health outcomes of interventions already in common clinical use;
3. The trial does not unjustifiably duplicate existing studies;
4. The trial design is appropriate to answer the research question being asked in the trial;
5. The trial is sponsored by a credible organization or individual capable of executing the proposed trial successfully;
6. The trial is in compliance with Federal regulations relating to the protection of human subjects; and
7. All aspects of the trial are conducted according to the appropriate standards of scientific integrity.

Qualification Process for Clinical Trials

Using the authority found in §1142 of the Act (cross-referenced in §1862(a)(1)(E) of the Act), the Agency for Healthcare Research and Quality (AHRQ) will convene a multi-

agency Federal panel (the "panel") composed of representatives of the Department of Health and Human Services research agencies (National Institutes of Health (NIH), Centers for Disease Control and Prevention (CDC), the Food and Drug Administration (FDA), AHRQ, and the Office of Human Research Protection), and the research arms of the Department of Defense (DOD) and the Department of Veterans Affairs (VA) to develop qualifying criteria that will indicate a strong probability that a trial exhibits the desirable characteristics listed above. These criteria will be easily verifiable, and where possible, dichotomous. Trials that meet these qualifying criteria will receive Medicare coverage of their associated routine costs. This panel is not reviewing or approving individual trials. The multi-agency panel will meet periodically to review and evaluate the program and recommend any necessary refinements to CMS.

Clinical trials that meet the qualifying criteria will receive Medicare coverage of routine costs after the trial's lead principal investigator certifies that the trial meets the criteria. This process will require the principal investigator to enroll the trial in a Medicare clinical trials registry, currently under development.

Some clinical trials are automatically qualified to receive Medicare coverage of their routine costs because they have been deemed by AHRQ, in consultation with the other agencies represented on the multi-agency panel to be highly likely to have the above- listed seven desirable characteristics of clinical trials. The principal investigators of these automatically qualified trials do not need to certify that the trials meet the qualifying criteria, but must enroll the trials in the Medicare clinical trials registry for administrative purposes, once the registry is established.

Effective September 19, 2000, clinical trials that are deemed to be automatically qualified are:

1. Trials funded by NIH, CDC, AHRQ, CMS, DOD, and VA;

2. Trials supported by centers or cooperative groups that are funded by the NIH, CDC, AHRQ, CMS, DOD and VA;
3. Trials conducted under an investigational new drug application (IND) reviewed by the FDA; and
4. Drug trials that are exempt from having an IND under 21 CFR 312.2(b)(1) will be deemed automatically qualified until the qualifying criteria are developed and the certification process is in place. At that time the principal investigators of these trials must certify that the trials meet the qualifying criteria in order to maintain Medicare coverage of routine costs. This certification process will only affect the future status of the trial and will not be used to retroactively change the earlier deemed status.

Medicare will cover the routine costs of qualifying trials that either have been deemed to be automatically qualified or have certified that they meet the qualifying criteria unless CMS's Chief Clinical Officer subsequently finds that a clinical trial does not meet the qualifying criteria or jeopardizes the safety or welfare of Medicare beneficiaries.

Should CMS find that a trial's principal investigator misrepresented that the trial met the necessary qualifying criteria in order to gain Medicare coverage of routine costs, Medicare coverage of the routine costs would be denied under §1862(a)(1)(E) of the Act. In the case of such a denial, the Medicare beneficiaries enrolled in the trial would not be held liable (i.e., would be held harmless from collection) for the costs consistent with the provisions of §1879, §1842(l), or §1834(j)(4) of the Act, as applicable. Where appropriate, the billing providers would be held liable for the costs and fraud investigations of the billing providers and the trial's principal investigator may be pursued.

Medicare regulations require Medicare+Choice (M+C) organizations to follow CMS's national coverage decisions. This NCD raises special issues that require some modification of most M+C organizations' rules governing provision of items and services in and out of network. The items and services covered under this NCD are inextricably linked to the

clinical trials with which they are associated and cannot be covered outside of the context of those clinical trials. M+C organizations therefore must cover these services regardless of whether they are available through in-network providers. M+C organizations may have reporting requirements when enrollees participate in clinical trials, in order to track and coordinate their members' care, but cannot require prior authorization or approval. For the initial implementation, Medicare contractors will pay providers directly on a fee for service basis for covered clinical trial services for beneficiaries enrolled in M+C plans.

Appendix D: Methods of Contraceptives

D1 Contraception requirement for all subjects who will not receive mycophenolate mofetil following transplantation.

The below listed methods meet the requirements for contraception as per the CTFG guidance.¹⁸

If female, subject must be either postmenopausal defined as:

- Age \geq 55 years with no menses for 12 or more months without an alternative medical cause.
- Age $<$ 55 years with no menses for 12 or more months without an alternative medical cause AND an FSH level $>$ 40 IU/L.

OR

● Permanently surgically sterile (bilateral oophorectomy, bilateral salpingectomy or hysterectomy).

*OR for Women of Childbearing Potential who **do not** receive mycophenolate mofetil immunosuppressant after kidney transplantation*

- Agreeing to practice one effective method of birth control while receiving G/P (as outlined in the subject information and consent form or other subject information documents), starting with Day of transplant and for at least 30 days after stopping G/P.
 - Progestogen-only hormonal contraception (oral, injectable, implantable) associated with inhibition of ovulation, initiated at least 1 month prior to Study Day 1.
 - Bilateral tubal occlusion/ligation.
 - Vasectomized partner(s), provided the vasectomized partner has received medical assessment of the surgical success and is the sole sexual partner of the WOCBP trial participant.
 - Non-ethinyl estradiol hormone-releasing Intrauterine device (IUD)
 - Non-ethinyl estradiol hormone-releasing Intrauterine hormone-releasing system (IUS)
 - Male or female condom with spermicide (male and female condom must not be used together)
 - Diaphragm with spermicide
 - Cervical cap with spermicide
 - Contraceptive sponge with spermicide

- True abstinence:
 - Refraining from heterosexual intercourse when this is in line with the preferred and usual lifestyle of the subject (periodic abstinence, e.g., calendar, ovulation, symptothermal, post-ovulation methods, “rhythm method,” or pre-ejaculation withdrawal, are not acceptable forms of contraception).
- Sexually active with female partners only

Male Subjects

Subject must be surgically sterile (vasectomy with medical assessment confirming surgical success)

OR

Have a female partner who is postmenopausal or permanently sterile (bilateral oophorectomy, bilateral salpingectomy or hysterectomy)

OR

if sexually active with female partner(s) of CBP must agree to practice one effective method of birth control while receiving G/P (as outlined in the subject information and consent form or other subject information documents), starting with Day 1 and for 30 days after stopping G/P.

- Any approved and commercially available hormonal contraception for female partners
- Any approved and commercially available, including any hormone-eluting, devices for female partners of male subjects
- Male or female condom with spermicide (male and female condom must not be used together)
- Female partner using a diaphragm with spermicide
- Female partner using a cervical cap with spermicide
- Female partner using a contraceptive sponge with spermicide
- True abstinence: Refraining from heterosexual intercourse-when this is in line with the preferred and usual lifestyle of the subject. (Note: Periodic abstinence (e.g., calendar, ovulation, symptothermal, post-ovulation methods, “rhythm method”, or pre-ejaculation withdrawal are not acceptable forms of contraception).
- Sexually active with male partners only

D2 Contraception requirements for all subjects who will receive mycophenolate mofetil post kidney transplant

All Women of child bearing potential subjects or male subjects with child bearing potential women partners who receive mycophenolate mofetil following kidney transplantation are required to utilize highly effective methods of birth control as per transplant center standard of care and consistent with the transplant center mycophenolate mofetil Risk Evaluation and Mitigation Strategy (REMS).

Appendix E: Extrahepatic Manifestations of HCV infection

Infection with hepatitis C virus (HCV) can lead to both acute and chronic hepatitis. The hepatitis C virus mainly affects the liver, but there are many other conditions that are associated with hepatitis C. Extrahepatic manifestation of HCV infection denotes diseases or conditions that affect organs other than the liver. Extrahepatic manifestations of hepatitis C infection can be found in the skin, eyes, joints, immune system, nervous system and kidneys.^{24,25} Some of the extrahepatic manifestations of HCV infection are more common- such as cryoglobulinemia, while others are not common. Furthermore, it is not well understood whether extrahepatic manifestations of HCV can already manifest during the phase of acute HCV infection. In this study the below listed diseases/conditions are recognized as extrahepatic manifestations of HCV infection and new onset/diagnosis of respective diseases/conditions following the transplant of an HCV-positive kidney during the study will be collected:

- Mixed cryoglobulinemia
- B cell non-hodgkin's lymphoma
- Monoclonal gammopathy
- Sjögren syndrome/sicca symptoms
- Polyarteritis
- Autoimmune thyroiditis
- Immune thrombocytopenia (ITP)
- membranoproliferative glomerulonephritis type 1
- Porphyria cutanea tarda
- Lichen planus

Summary of Statistical Analysis Plan for MYTHIC Study

[Draft: April 26, 2020]

Part	Patient Group(s)	Outcome	Statistical Analysis ^a
1	Arm 1 (ITT)	SVR12	- estimated probability of SVR12 and 95% confidence interval (CI) - exact binomial calculations
2	Arm 1 (ITT)	Virologic failure (VF)	- estimated probability of SVR12 and 95% confidence interval (CI) - exact binomial calculations
3	Arm 1 (ITT)	Post-treatment virologic relapse	- estimated probability of SVR12 and 95% confidence interval (CI) - exact binomial calculations
4	All patients	HCV-viremic kidney transplant (KT); i.e., Arm 1 KT	- cumulative incidence and 95% CI - death and other KT types treated as competing risk - estimate non-parametrically, using Lin (1997) which proceeds through the cause-specific hazards, or Fan (2013) which uses Inverse Probability of Censoring Weighting (IPCW).
5	All patients	Non-HCV-viremic KT; i.e., Arm 2A-2B KT	- same as for component (4).
6	All, by Arm	Hospital admissions	- Arm treated as a time-dependent treatment - crude hospitalization rate per 100 patient-years (PY) and 95% CI - use robust variance estimator, to account for correlation among hospital admissions within-patient
7	All, by Arm	Hospital admissions	- Arm treated as a time-dependent treatment - proportional rates model (Lin et al., 2000) - robust SEs, to account for clustering within-patient
8(a)	All, and SRTR* controls	Kidney transplant	- exclude, from SRTR, all patients who indicated consent to receive an HCV-viremic KT (hereafter: SRTR*) - estimate prognostic score using SRTR* patients: KT as event - 1:5 matching (MYTHIC : SRTR*) based on prognostic score with caliper - Cox regression, with MYTHIC as lone covariate, stratified by matched set

8(b)	All, and SRTR* controls	Kidney transplant	Same as 9(a), but using exact matching on small set of predictors, with prognostic score used to break ties among potential matches
9	Arm 1 – ITT	Compliance	Treated as repeated binary (0/1) data, with 1 indicating compliance (i.e., having taken 80-120% of prescribed pills)
10	Arm 1 – ITT	Death	Time to event; Cox regression
11	Arm 1 – ITT	Graft failure	Time to event; Cox regression
12	Arm 1	Delayed graft function	DGF: binary (0/1) response. Compute OBS/EXP, where OBS=observed number of DGFs for Arm 1 and EXP= expected count based on logistic regression model fitted to HCV-negative UNOS patients from large academic centers
13	Arm 1	Acute allograft rejection	AAR: Binary (0/1) response. Compute OBS/EXP, where OBS=observed number of AARs for Arm 1 and EXP= expected cunt based on logistic regression model fitted to HCV-negative UNOS patients from large academic centers
14	Arm 1	ALT elevation	Binary (0/1), with '1' corresponding to peak ALT > 5 x ULN, where ULN=upper limit of 'normal'.
15	All, by arm	Serious Adverse Event	SAE: recurrent event Arm treated as a time-dependent factor Proportional rates model, robust SEs to account for within-patient clustering
16	Arm 1, 2AB	eGFR	Repeated continuous response Linear mixed model, to account for clustering by patient
17	Arm 1, 2AB	Proteinuria	Binary response; logistic regression
18	Arm 1, 2AB	BK virus	Binary response; logistic regression

Notes:

a) Each of the above-listed analyses will be accompanied by appropriate summary statistics (e.g., mean, median, IQR, etc).

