5.3.2.2 Secondary Efficacy Variables

The secondary efficacy endpoints will be calculated among subjects receiving study eligible HCV-RNA-positive kidneys treated with G/P (Arm 1).

- The percentage of subjects with on-treatment virologic failure;
- The percentage of subjects with post-treatment relapse.

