8.1.2.2 Secondary Efficacy Endpoints

The secondary efficacy endpoints to be summarized for all ITT subjects who are:

- the number and percentage of subjects with on-treatment virologic failure (confirmed increase of $> 1 \log_{10}$ IU/mL above nadir during treatment, confirmed HCV RNA ≥ 100 IU/mL after HCV RNA $<$ LLOQ during treatment, or HCV RNA \geq LLOQ at the end of treatment with at least 6 weeks of treatment);
- the number and percentage of subjects with post-treatment relapse (defined as confirmed HCV RNA \geq LLOQ between end of treatment and 12 weeks after the last dose of study drug among subjects who completed treatment as planned with HCV RNA $<$ LLOQ at the end of treatment, excluding subjects with reinfection).

For the analysis of relapse, completion of treatment is defined as any subject with study drug duration of 49 days or greater for 8-week treatment.

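### SAP Parts 2 and 3 name SVR12 as the quantity to estimate for virologic failure and relapse, drop the on-treatment qualifier, and leave the relapse denominator unsettled

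*SAP*

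**What the plan says.** The SAP is a summary table marked as a draft. Parts 1, 2 and 3 all use the group Arm 1 (ITT), and their analysis cells are identical: "estimated probability of SVR12 and 95% confidence interval (CI", by "exact binomial calculations". Only the outcome changes: SVR12 in Part 1, "Virologic failure (VF" in Part 2, and "Post-treatment virologic relapse" in Part 3. A general note adds: "Each of the above-listed analyses will be accompanied by appropriate summary statistics".

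Protocol 5.3.2.2 lists two secondary efficacy endpoints for Arm 1: "The percentage of subjects with on-treatment virologic failure" and "The percentage of subjects with post-treatment relapse". Section 8.1.2.2 defines each event and asks for its number and percentage. Its lead-in assigns both endpoints to the whole ITT population. Its relapse definition is narrower: relapse is counted "among subjects who completed treatment as planned with HCV RNA" below LLOQ at the end of treatment, with reinfection excluded. Completion means at least 49 days of study drug.

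**The concern.** The analysis column tells the programmer what to compute. In Parts 2 and 3 it names a quantity that is neither protocol endpoint. These are the only two secondary efficacy endpoints, and the SAP says nothing else about how to count either event.

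Two further gaps sit in the same rows:

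- Part 2 omits the on-treatment qualifier. Protocol 8.1.2.2 keeps on-treatment failure and relapse apart. Section 8.1.2.3, however, uses VF in the name of a population whose qualifying failures are both on-treatment failure and relapse. An analyst could therefore count relapses in Part 2 and again in Part 3.
- Part 3 does not say whether the relapse percentage is taken over all ITT subjects or over those who could relapse as 8.1.2.2 defines it.

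**Working it through.** **No plan figure to reproduce.** The documents give no expected rate, sample size or power for either endpoint. The check sets the texts side by side and then sizes the effect on assumed counts.

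**Side by side**

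| | Protocol 8.1.2.2 | SAP |
|---|---|---|
| Failure: event | On-treatment virologic failure, defined | Virologic failure, undefined |
| Failure: estimate | Number and percentage with the event | Probability of SVR12 |
| Failure: group | ITT | Arm 1 (ITT) |
| Relapse: event | Confirmed, within 12 weeks of last dose, reinfection excluded | Relapse, undefined |
| Relapse: estimate | Number and percentage with the event | Probability of SVR12 |
| Relapse: group | Lead-in: ITT. Definition: at least 49 days of drug and HCV RNA below LLOQ at end of treatment | Arm 1 (ITT) |

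The failure row has no population error. The relapse group is unsettled in the protocol itself, and the SAP does not settle it. Protocol 5.5.1.1 also describes relapse, for retreatment purposes, without stating confirmation, the 12-week limit or the reinfection exclusion. The SAP should say which definition it uses.

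**Inputs.** N = 30 (protocol 8.2); two-sided 95% intervals (protocol 8.1); exact binomial method (SAP). The outcome split is assumed and is not in the documents: 26 with SVR12, 1 on-treatment failure, 1 relapse, and 2 who stopped before 49 days without SVR12 (26 + 1 + 1 + 2 = 30). The subjects at risk of relapse are then 30 − 1 − 2 = 27.

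**Formula.** For x events in n, the Clopper-Pearson limits are the 2.5% quantile of Beta(x, n − x + 1) and the 97.5% quantile of Beta(x + 1, n − x). With x = 0 the lower limit is 0.

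**Effect of the wrong estimate**

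- Parts 2 and 3 read literally: 26/30 = 86.7% (69.3 to 96.2), the Part 1 result again.
- On-treatment failure as the protocol defines it: 1/30 = 3.3% (0.1 to 17.2).
- Relapse on the at-risk set: 1/27 = 3.7% (0.1 to 19.0).

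Subtraction does not recover either endpoint. Here 1 − 26/30 = 4/30 = 13.3%, which mixes failure, relapse and early stopping.

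**Effect of the dropped qualifier.** If Part 2 counted the relapse too, it would give 2/30 = 6.7% (0.8 to 22.1) instead of 3.3%.

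**Effect of the relapse denominator**

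| Denominator | 1 relapse | 0 relapses, upper limit |
|---|---|---|
| 30 (all ITT) | 3.3% (0.1 to 17.2) | 11.6% |
| 27 | 3.7% (0.1 to 19.0) | 12.8% |
| 25 (5 subjects not at risk) | 4.0% (0.1 to 20.4) | 13.7% |

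**The case against.** The strongest reply is that this is a clerical slip that no analyst would follow. The outcome column names the right events, in the order of the protocol synopsis. The document is a draft summary with other slips: Part 8(b) refers to a Part 9(a) that does not exist. Protocol 8.1.2.1 separately asks for the reasons for SVR12 non-response, naming on-treatment failure and relapse. Relapse has its own row directly below Part 2, which suggests that Part 2 means on-treatment failure.

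Much of this stands. A reader might infer that neither secondary efficacy endpoint will be produced. The documents do not support that, because the outcome column and protocol 8.1.2.2 show what was meant. The slip still sits in the operative column, and unspecified summary statistics under the general note do not supply the correct estimate.

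A reader might also infer that putting relapse on ITT contradicts the protocol. It does not. Section 8.1.2 makes ITT the default for efficacy, and the lead-in of 8.1.2.2 applies it to both endpoints. The completer restriction lies inside the relapse definition and can be read as defining either the event or the denominator. The fair criticism is that the SAP leaves this open.

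**Conclusion.** The SAP is wrong as written in the estimate named for both secondary efficacy endpoints, most likely through text carried over from Part 1. Read literally, it changes the reported quantity entirely: 86.7% in place of 3.3% and 3.7% in the assumed split. The missing on-treatment qualifier is a smaller, real ambiguity.

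The denominator question is minor. It moves one relapse from 3.3% to 3.7% or 4.0%, less than one percentage point, and the intervals overlap almost entirely. All percentages rest on assumed counts; the textual mismatch does not. The primary SVR12 result is untouched, and protocol 8.2 describes a feasibility study that generates preliminary data. This should be corrected before the SAP is final, as a drafting correction and not as a challenge to the design.

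**What to change.** Rewrite two analysis cells and settle one denominator:

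- **Part 2:** *estimated probability of on-treatment virologic failure (protocol 8.1.2.2), Arm 1 ITT, 95% CI*.
- **Part 3:** *estimated probability of post-treatment relapse (protocol 8.1.2.2), 95% CI; denominator: Arm 1 ITT subjects with at least 49 days of G/P and HCV RNA below LLOQ at end of treatment, excluding reinfection*.
- **Reconciliation:** add a sentence explaining how this denominator fits the lead-in of 8.1.2.2, which speaks of the whole ITT population. The SAP can carry it, since protocol 8.1 leaves analysis details to the SAP.
- **Interval method:** use the one chosen for SVR12. The protocol names Wilson's score and the SAP exact binomial, so that choice should be made once and applied to all three parts.

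The cost is two rows and a sentence in a draft document. Study drug duration and HCV RNA results are already collected, so no new data are needed.
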